The proposed study takes this next step. Specifically, the treatment to be developed and tested in this grant, "B-FIT" (Brief Family-Involved Treatment), is designed as an add-on to community-based substance abuse treatment-as-usual (TAU). B-FIT uses family involvement to enhance patient treatment adherence and outcomes by improving family functioning and increasing family-provided incentives for treatment adherence and abstinence. Study aims are carefully sequenced to develop the B-FIT treatment and judge its merits.

Figure 1. Proposed relations among B-FIT active ingredients, mediators, and outcomes

OBJECTIVES/AIMS/HYPOTHESES

The overall study has three specific aims:

Aim 1. To modify our existing ABCT model to make it (a) appropriate for any concerned family member, (b) shorter, (c) focused on key mechanisms of change identified in prior research, (d) appropriate for use as part of an on-going alcohol treatment program, and (e) more efficacious by incorporating behavioral contracting procedures (O'Farrell & Fals-Stewart, 2000; Smith & Meyers, 2004).

Aim 2. To conduct a small-scale clinical trial of B-FIT to: **Aim 2a.** Obtain preliminary effect-size estimates of the impact of B-FIT on (a) patient treatment adherence; (b) drinking outcomes; (c) family functioning; and (d) functioning of the concerned family member. **Aim 2b.** Obtain estimates of the disseminability of the protocol by assessing: (a) clinicians' ability to learn and implement the

intervention; (b) clinician evaluations of the ease of protocol implementation; (c) patient and family member feedback about B-FIT; and (d) the proportion of patients and concerned family members willing to participate in the intervention. **Aim 2c.** Develop and conduct a preliminary test of a methodology to study the active ingredients in the B-FIT treatment and purported mechanisms by which it works. **Aim 2d.** Test major moderators of the treatment effect: (a) demographic variables and severity of AUD; (b) individual psychological variables; and (c) familial distress/support.

Aim 3. Finalize materials for a larger-scale RCT, including: (a) treatment manual; (b) patient and family manuals; (c) clinician training materials; (d) a treatment integrity rating system; (e) all measures.

The focus of this IRB application is the pilot study and randomized clinical trial. We were previously approved for the focus group portion of the study in IRB application 01815.

STUDY DESIGN AND PROCEDURES

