All data collected by a research assistant on site will be transported from TLH to the CASAA research offices in a briefcase or similar closed storage medium—loose papers or papers in open folders will not be allowed. After returning to the research office, all hard copy data will be stored in a locked file cabinet. Audio recordings will immediately be transferred onto a computer and deleted from the digital recorder. All computerized data (including audio recordings) will be stored on the CASAA server, which is firewall protected, and accessible only through individual authorization and passwords. Audio recordings will be reviewed in closed rooms at the lowest reasonable volume or with headphones. Data will be retained for publication purposes for five years following the last study publication, per usual data retention standards.

Data collected from this project will be available only to selected research staff. Data will be collected by research staff and shared with treatment staff only if there is a need in order to protect patient or family member safety. For example, if during the baseline assessment a research staff member finds out that a participant has current suicidal ideation, we would share this with a clinician because this could have material effect on the participant's well being. Other than those contingencies only the research staff composed of the research assistants, co-investigators and the PI will have continuing access to participant data. Similarly, disclosures of child abuse or neglect will, by law, be reported to the CYFD.

II. Data Analysis/Statistical Considerations

Statistical power. The R34 mechanism is developmental in nature and for this reason substantial emphasis in this application is placed upon both inferential testing and the estimation and evaluation of effect sizes. Our test of the efficacy of the B-FIT intervention after anticipated attrition (15%; Aim 2a) will include 34 participants in the B-FIT group and 17 in TAU and test outcomes both for

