percentage of days abstinent (PDA) and percentage of days of heavy drinking (PDH). We believe that this is a conservative estimate given the method in which the planned HLM handles missing data. In a two-tailed test adjusted for conducting correlated tests of drinking behavior over time ($\alpha = .05/2 = .025$), the baseline dependent measure entered as a fixed covariate and 1 *df* for the between-group term, we estimate that we will have .703 power to reject the null hypothesis of no difference between TAU and TAU + B-FIT with 51 participants and an effect size of .20 ($d = .25$ to achieve power of .80).

Statistical analyses. An extensive set of analyses is proposed that includes the assessment of treatment fidelity, document CFM and patient satisfaction with the B-FIT intervention, and examine outcomes in general, mechanisms of change, and potential moderators of treatment response. Initial attention will be directed to investigating overall and between-group attrition rates and distributions of key measures prior to conducting primary analyses. Although quantitative support will be provided in the achievement of all study Aims, the described statistical analyses will focus on the stated objectives in study Aim 2a, 2c, and 2d, which are central to the proposed model (Figure 1).

Aim 2a. Obtain estimates of the relative impact of B-FIT on patient treatment adherence, drinking outcomes, family functioning, and functioning of the CFM. Treatment adherence will be defined as the total number of TAU sessions attended between randomization and the 4-month follow-up interview (measured by the TSR and Form-90). Two primary alcohol use measures will be considered and aggregated into four monthly values: proportion abstinent days from alcohol (PDA: days abstinent/ 30 days) and percentage of days of heavy drinking (PDH). Family functioning will be assessed using the Cohesion and Conflict subscales of the Family Environment scale, and the Family Communication scale total score. CFM functioning will be defined as total scores on the Beck Depression Inventory (BDI) and Beck Anxiety Inventory (BAI).

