Generalized linear models (GLM) will assess the relative benefit of the B-FIT intervention to TAU alone on treatment adherence, family, and CFM functioning. Parameter estimates will be derived using maximum likelihood with robust estimators. In the treatment adherence GLM, two covariates are planned: number of TAU sessions attended *prior* to randomization and baseline PDA. The dependent measure will be the total number of TAU sessions attended from randomization to the 4-month follow-up and treatment assignment will be entered as a between-subject factor. A two-tailed test will be done with Type I error set at $\alpha = .05$. Four GLMs will be used to assess the relative benefit of B-FIT on family functioning; two using the patient 4-month report of family Cohesion and Conflict and two based upon CFM 4-month report of family Cohesion and Conflict. Baseline values of the two scales will be used as covariates. Treatment group will be entered into the model as a between-subject factor and Type I error will be adjusted to $\alpha = .05/2 = .025$ in the two-tailed tests. The relative benefit of B-FIT on CFM functioning will be determined using two GLMs. The first GLM will use 4-month BDI scores as the dependent measure and baseline values of the BDI will be entered as a covariate. Baseline values of PDA for the CFM also will be entered as a covariate to negate any influence of drinking on self-reported depression. Treatment assignment will be entered as a between-subject factor. A second GLM following the same strategy then will use the 4-month BAI score as the dependent measure. These tests of CFM functioning will be adjusted by $\alpha = .05/2 = .025$ to control for inflated Type I error.

The relative benefit of adding the B-FIT sessions to TAU on drinking over four months will be determined using two longitudinal hierarchical linear models, one for PDA and a second for PDH (Raudenbush & Bryk, 2002). Modeling of change in alcohol use will be restricted to the linear effect given the limited number of time points. The random intercept in the unconditional models will be examined first, followed by fitting the conditional models, which will introduce baseline value of the respective drinking measure (PDA or PDH) as a fixed covariate and the random linear time term. Treatment group will then be entered in level two of the model and will be tested via the *t*-statistic.

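### The two printed power figures (.703 at .20, .80 at d = .25) cannot both come from one d-scale or f-scale calculation of the 1-df group test, and the metric, method and correlations are not given

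*Combined protocol and SAP*

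**What the plan says.** All the power inputs are in the combined protocol and SAP, under Study Data, II. Data Analysis/Statistical Considerations, in the Statistical power paragraph.

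- **Sample:** the efficacy test "after anticipated attrition (15%; Aim 2a) will include 34 participants in the B-FIT group and 17 in TAU", which makes 51.
- **Test:** two-tailed, alpha .05/2 = .025, with "the baseline dependent measure entered as a fixed covariate and 1 *df* for the between-group term".
- **Result:** .703 power ("703 power to reject the null hypothesis of no difference between TAU and TAU + B-FIT with 51 participants"); the sentence goes on to the effect sizes, "with 51 participants and an effect size of .20 ($d = .25$ to achieve power of .80". The symbol d stands beside .25 only; the .20 has no symbol.

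Under Statistical analyses, Aim 2a, PDA and PDH are each "aggregated into four monthly values" and analysed in a hierarchical linear model with the baseline value as a covariate. "Treatment group will then be entered in level two of the model and will be tested via the *t*-statistic"; a time-by-group term is then tested as well.

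Neither paragraph gives a formula, software, a standard deviation, a baseline-to-outcome correlation or a between-month correlation.

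**The concern.** Fifty-one patients split 2:1 is a small sample, and d values of .20 and .25 are small effects. Power of 70 to 80% for such effects at two-sided .025 looks implausible on sight. The step from .703 to .80 is also too small for a 25% increase in effect size.

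This is the only power statement for the PDA and PDH comparison. The plan says that "substantial emphasis in this application is placed upon both inferential testing and the estimation and evaluation of effect sizes", so the inferential side matters to its readers. Someone who takes the sentence at face value would think the trial had a good chance of detecting a small effect, and could read a non-significant PDA or PDH result as evidence against one. The consequence is limited because Aim 2a is to "Obtain preliminary effect-size estimates of the impact of B-FIT", and the documents tie no decision rule to the power figure.

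**Working it through.** **Inputs from the plan.** n = 34 and 17, N = 51; two-sided alpha .025; 1-df group term; one baseline covariate, so about 48 residual df; four monthly values. **Assumed, because not given:** between-month correlation rho and the share R² of outcome variance explained by baseline. All powers use the noncentral F distribution.

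**1. Reproducing the printed figure.** The closest reading takes .20 and .25 as f² for an overall F test of two predictors (baseline and group) on (2, 48) df, with lambda = N × f².
- f² = .20: lambda = 51 × .20 = 10.2, power .703.
- f² = .25: lambda = 51 × .25 = 12.75, power .812. Power .80 is reached at f² = .244, close to the printed .25.

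The documents state no method, so this is an inference. It is also not the stated test, which has 1 df. On 1 df with the same lambda, power depends on how much of f² = .20 belongs to group: 25% gives .25, 50% gives .48, 75% gives .67 and 100% gives .81.

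**2. Do the two figures fit one d or f scale?** On either scale lambda is proportional to the effect size squared. rho and R² enter only as a constant multiplier, which cancels from the ratio.
- On (1, 48) df, power .703 needs lambda = 8.119 and power .80 needs lambda = 10.027.
- Starting from .703 at .20: at .25, lambda = 8.119 × (.25/.20)² = 8.119 × 1.5625 = 12.69, power .89.
- Effect size for .80: .20 × √(10.027/8.119) = .222, not .25.
- Starting from .80 at .25: at .20, lambda = 10.027/1.5625 = 6.42, power .59.

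**3. d scale, single outcome.** lambda = d² × (34 × 17)/51 = 11.333 d².
- d = .20: lambda = .453, power .058.
- d = .25: lambda = .708, power .079.
- Power .80 needs d = √(10.027/11.333) = .94.

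**4. d scale, crediting the repeated measures and the covariate.** For the mean of four months the variance is multiplied by v = [(1 + 3 rho)/4] × (1 − R²), and lambda = 11.333 d²/v.
- Assumed rho .3 to .7 and R² .25 to .50: power about .08 to .19 at d = .20 and .12 to .29 at d = .25.
- For .703 at d = .20, v must be .453/8.119 = .0558. With independent months (rho = 0), R² = 1 − 4 × .0558 = .78.
- For .80 at d = .25, v must be .708/10.027 = .0706. With rho = 0, R² = 1 − 4 × .0706 = .72.

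**5. f scale.** With four independent months and no covariate gain, lambda = 51 × f² × 4. At f = .20 this is 8.16, power .705, which is close to .703. At f = .25 it is 12.75, power .89, not .80.

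**The case against.** The strongest reply is that this is a mislabelled metric and not a power shortfall. The f² reading uses the stated N and alpha and the two predictors in the model, and it comes close to both printed numbers. If it is right, the defects are the symbol d and the numerator degrees of freedom. If all of that f² were group effect, the 1-df power would be .81, so .703 would understate it. This stands as a possible explanation. It does not rescue the sentence, which claims power for the 1-df group term and labels .25 as d. An overall F test also credits the covariate's own effect.

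Three stronger conclusions are tempting and should not be drawn.

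- *The trial has 6 to 8% power, or the printed figures are impossible.* The .20 carries no symbol, and extreme unstated inputs could give either figure alone on the d scale (for example independent months with baseline R² of .78 or .72). What holds is that plausible correlations do not reproduce them and that no single set gives both.
- *The trial is powered only for a large effect.* f² = .20 equals d = √(.20/(2/9)) = .95 at 2:1 only if baseline explains nothing. If group supplies 25% or 50% of that f², the group d is about .47 or .67.
- *The assumed rho and R² ranges are planning values.* They are illustrations. If baseline shares the between-month correlation, the two move together, with v = (1 + 3 rho)/4 − rho². For rho 0 to .8, power is then .12 to .21 at d = .20 and .18 to .33 at d = .25, still far below the stated figures.

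The developmental purpose of the grant also limits the consequence.

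**Conclusion.** The concern holds in a limited form. The power sentence cannot be re-derived from what the plan gives, and its two figures are inconsistent with each other on any d or f scale: .89 instead of .80 at .25, or .59 instead of .703 at .20. That result needs no assumption about rho or R².

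On the d scale, power for the planned group term is .058 and .079 for a single outcome. It is about .08 to .19 and .12 to .29 for a four-month mean with baseline adjustment, which rests on the assumed rho of .3 to .7 and R² of .25 to .50. On the inferred f² reading, the 1-df power may lie below or above .703, depending on the share of the effect that belongs to group. The documents do not settle which metric was meant, so the size and direction of the error stay open. The statement should be corrected. It does not invalidate the design, which mainly serves preliminary effect-size estimation.

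**What to change.** In the Statistical power paragraph, replace both the .703 and the d = .25 statements with the power, or the minimum detectable effect, for the 1-df group term at 34 vs 17 and two-sided .025. State with it:

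- the effect-size metric, for every value quoted;
- the tested term (four-month mean or time by group);
- the assumed between-month correlation;
- the assumed baseline R²;
- the formula or software.

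If f² was meant, say so, remove the label d and recompute on 1 df for the group effect alone. Reporting the PDA and PDH effects with 97.5% confidence intervals would be a useful but optional addition.

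The cost is wording only. Enrolment and the planned models do not change, and the correction can be made before the analysis period in Study Timelines (December 2017 to March 2018). The drawback is that, if d was meant, the stated power becomes much less favourable.

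### Aim 2a tests nine group effects in four outcome domains as relative benefit, and does not say that only PDA and PDH can carry an efficacy claim

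*Combined protocol and SAP*

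**What the plan says.** All references are to STUDY DATA, II. Data Analysis/Statistical Considerations.

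Aim 2a is introduced as follows: "Obtain estimates of the relative impact of B-FIT on patient treatment adherence, drinking outcomes, family functioning, and functioning of the CFM". The tests of treatment group are:

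- **Adherence:** one GLM on the number of TAU sessions attended. "A two-tailed test will be done with Type I error set at" .05.
- **Family functioning:** "Four GLMs will be used to assess the relative benefit of B-FIT on family functioning" (Cohesion and Conflict, each reported by patient and by CFM), with .05/2 = .025 per test.
- **CFM functioning:** two GLMs (BDI and BAI), each at .025.
- **Drinking:** "The relative benefit of adding the B-FIT sessions to TAU on drinking over four months will be determined using two longitudinal hierarchical linear models". PDA and PDH have separate models, each tested at .025. Time-by-group interactions are also tested in these models.

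The three non-drinking domains are introduced together: "Generalized linear models (GLM) will assess the relative benefit of the B-FIT intervention to TAU alone on treatment adherence, family, and CFM functioning". Drinking is described in the same relative-benefit terms.

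On ranking, the Statistical power paragraph presents the efficacy test as a test of PDA and PDH and gives power for those two only. The Aim 2a text adds: "Two primary alcohol use measures will be considered and aggregated into four monthly values". On purpose, the same power paragraph says that "substantial emphasis in this application is placed upon both inferential testing and the estimation and evaluation of effect sizes".

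**The concern.** Error is controlled inside each domain, but no statement connects the domains: there is no overall rate, no order, and no secondary label for adherence, family or CFM outcomes. The word primary in Aim 2a is attached to alcohol use measures, so it can be read as primary among the drinking measures rather than primary for the trial.

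Other aims are more explicit. Aim 2c says that its six mediation tests are unadjusted. Aim 2d is called exploratory, admits inflated Type I error, and places drinking first with family satisfaction as secondary. Aim 2a has no such sentence. Aim 2c also asks why the benefit of B-FIT occurred without saying which domain establishes that benefit, and adherence is an outcome in Aim 2a but a mediator of PDA in Aim 2c.

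The domains can disagree. A significant CFM anxiety result with no drinking effect could be reported as a demonstrated benefit and carried into the case for the larger RCT.

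**Working it through.** **Inputs from the plan.** One test at .05 and eight at .025 (4 family + 2 CFM + 2 drinking). The plan's own adjusted level reproduces: .05/2 = .025.

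**Sum of alphas by domain.** Adherence .05. CFM 2 × .025 = .05. Drinking group terms 2 × .025 = .05. Family 4 × .025 = .10, because a divisor of 2 is applied to four tests. Total .25, which is the upper bound under any correlation.

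**If drinking alone decides.** The error for the two group terms is 1 − .975² = .049 under independence and at most .05 under any correlation. If the two time-by-group interactions also counted at .025, it would be 1 − .975⁴ = .096 under independence.

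**If any of the nine group tests could decide, global null, independence.** 1 − .95 × .975⁸ = .224. This splits into:

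- at least one false positive in drinking: .049;
- none in drinking but at least one elsewhere: .975² × (1 − .95 × .975⁶) = .951 × .184 = .175.

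Most of the excess therefore lies outside the drinking domain. Adding the two interactions at .025 gives 1 − .95 × .975¹⁰ = .262.

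**With correlation (assumed; the documents give none).** Simulation of nine jointly normal two-sided test statistics, 1,000,000 draws per case:

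| Within-domain r | Between-domain r | At least one false positive |
|---|---|---|
| .3 | 0 | 22% |
| .3 | .3 | 20% |
| .5 | .3 | 19% |
| .5 | .5 | 17% |
| .7 | .3 | 18% |
| .8 | .5 | 15% |
| .9 | .5 | 14% |
| .7 | .7 | 13% |
| .9 | .9 | 8% |

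With between-domain r of .3 to .5 and within-domain r of .3 to .9, or r = .7 throughout, the rate is about 13-20%. Independent domains put it at 16% (within-domain r = .9) to 22%. The last row treats BDI, session counts and drinking as near-duplicates. It is shown as an extreme, and it is still above 5%.

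**What Holm gains in a pair.** Under Holm the smaller p-value is compared with .025 and, if it passes, the other with .05. Familywise error stays at or below .05, and every rejection made at fixed .025 is kept. For illustration, take power of .70 for each test at .025, close to the plan's stated .703 (used here without endorsing that figure). The power of each test at .05 is then .790. With independent tests, Holm gives .70 + (.790 − .70) × .70 = .763, a gain of about 6 points. At correlation .9 the simulated value is .739, a gain of about 4 points.

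**The case against.** The strongest reply is that the plan has already chosen. The power paragraph ties efficacy to PDA and PDH, corrects for two tests and sizes the trial on them. No other domain is powered or called an efficacy test. Aim 2d, though a different aim, shows the same drinking-first order. On this reading the efficacy error is at most 5%. This stands, and it limits the point to a missing explicit statement. A reader might infer that the plan has no deciding outcome, or that its efficacy conclusion carries a 22% false-positive rate. The documents do not support that: the 22% applies only if any of the nine tests could establish efficacy.

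Second, this is a developmental study seeking preliminary effect sizes. Each benefit is worded by domain, and Aim 3 finalises the RCT materials without any significance condition. So one error rate across all four domains is not required, and asking for it would be close to a preference. What remains is that the plan says it emphasises inferential testing as well as estimation, and already adjusts for multiplicity inside Aim 2a. It should therefore say what the remaining tests are for.

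Third, a reader might think that the small, unequal groups (34 and 17 after attrition) make chance findings outside drinking more likely. They do not: nominal false-positive rates depend on the alphas, the number of tests and their correlation, not on sample size.

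**Conclusion.** The point holds as a gap in the statement of the decision rule. The plan points to PDA and PDH as the efficacy test but does not say that adherence, family and CFM results cannot carry that claim. If they could, the chance of at least one false positive among the nine group tests is about 22% under independence, and about 13-20% over the main range of correlations assumed. Both figures rest on a global null and on correlations that are not in the documents; counting the time-by-group interactions would raise them. If the plan's apparent intention is made explicit, the efficacy error is at most 5% with no change to the design. The Holm step is a separate improvement, not the repair of an error: the fixed .05/2 already controls each pair.

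**What to change.** 1. Add to the Aim 2a analysis text, in substance:

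> Efficacy of B-FIT is decided by the treatment-group terms in the PDA and PDH models only, at a familywise two-sided .05. The time-by-group interactions in these models are outside that decision. Adherence, family functioning and CFM functioning are secondary. They are reported as estimates with confidence intervals and nominal p-values, and do not by themselves support a claim of efficacy.

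2. In the PDA/PDH pair and the BDI/BAI pair, replace the fixed .05/2 with Holm: .025 for the smaller p-value and, if that is significant, .05 for the other. Familywise error in each pair is unchanged and power is never lower.

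**Cost.** A few sentences; no new data, measures or patients. The downside is that an adherence, family or CFM result standing alone can no longer be called proof of efficacy. That fits both the plan's power basis and Aim 2a's stated purpose of estimating effects.

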Initial screening. Patients will be screened in person or over the phone by study personnel. A simple checklist will be used to determine eligibility criteria related to date of treatment entry, age, and methadone maintenance status. AUD diagnosis will be assessed using the substance abuse module of the SCID interview (First et al., 2002). Psychotic symptoms will be assessed using the psychotic screening questions from the SCID (<http://www.scid4.org>). Presence of domestic violence will be assessed using the Partner Violence Screen (Feldhaus et al., 1997). These measures are all included in the B-FIT Screening interview. If eligible, the patient will be provided with a brief description of the study, will be asked to provide the name of an eligible CFM and verify frequency of contact and perceived importance (using one item from the Important People Interview, Longabaugh & Zywiak (1999), and will sign a release of information to allow study personnel to contact the family member and will be asked to mention study participation to the family member.

CFMs will be screened in person or over the phone by study personnel. A simple checklist will be used to assess family member age, frequency of contact with the patient, and current help-seeking status. Presence of domestic violence will be assessed using the Partner Violence Screen (Feldhaus et al., 1997). Psychotic symptoms will be assessed using the psychotic screening questions from the SCID (<http://www.scid4.org>). Severity of alcohol use will be assessed with the AUDIT (Saunders, Aasland, Babor, de la Fuente, & Grant, 1993); a score of 8 or greater will exclude the CFM from the study. Severity of drug dependence will be assessed with the DAST-10 (Skinner, 1982); a score of 3 or greater will exclude the CFM. If eligible, the family member will be provided with a brief description of the study, and asked about willingness to participate.

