Baseline assessment. Baseline assessments with patients and CFMs will be conducted by staff from the CASAA Program Evaluation Service (PES). Screening and baseline measures assess inclusion/exclusion criteria; locator and tracking information, sociodemographic descriptors, potential moderator variables; alcohol and other drug use, consequences, and diagnosis; CFM functioning and baseline measurement of hypothesized mediators of response to treatment (see Table 1). Each individual will be interviewed separately, and the patient and CFM may be scheduled at different or the same times for their baseline interviews. Patient baseline data collection will take approximately 2.5 hours; CFM baseline data collection will take approximately 1.25 hours. Patients will be compensated \$50; CFMs will be paid \$30.

Randomization. After the baseline interview, couples will be randomly assigned to TAU or TAU+B-FIT using urn randomization (Stout, Wirtz, Carbonari, & Del Boca, 1994) to balance groups on patient gender, severity of alcohol dependence, and type of CFM (parent versus partner versus other).

Treatment Conditions

Treatment as usual (TAU). Turquoise Lodge Hospital (TLH) provides detoxification services and residential treatment to adults with substance use disorders. The average residential stay is 18-21 days. TLH is currently developing an intensive outpatient program from which we also plan to recruit. **TAU at TLH consists of mainly group and some individual therapy.** Families do not typically participate in treatment but are allowed to visit patients during designated weekend hours.

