Cross-level interactions will be tested via the *t*-statistic to identify potential time by group interactions in changes in alcohol use. Type I error will be adjusted to $\alpha = .05/2 = .025$ to account for the correlation between PDA and PDH.

Aim 2c. This aim will investigate whether the relative benefit of B-FIT occurred for the presumed reasons. As such, this aim will focus only on participants assigned to the B-FIT group ($n = 40$ at baseline). Tests of mediation will use a product-of-coefficients approach with a bootstrapping procedure (Hayes, 2009). This choice provides the most powerful test of mediation with smaller samples and does not assume normality in the distribution of ($a'b'$) product terms (Preacher and Hayes, 2008; Hayes, 2009). Three active ingredients of B-FIT will be investigated separately: (1) teaching skills to reinforce change, (2) teaching skills to increase positive exchanges, and (3) teaching skills to improve communication, all of which are measured within treatment by the modified C-TIRS. Baseline values of mediators will be entered into all planned analyses as covariates. Overall, we will conduct six mediational tests. First, we will conduct 3 mediational tests to evaluate our prediction that teaching skills to reinforce change will increase 4-month abstinence (PDA) by mobilizing three mediators during the treatment phase of the study (TAU treatment adherence, commitment to abstinence, and perceived family support). The fourth test will examine if teaching skills to reinforce change increases family satisfaction (month 4) through enhanced impressions of perceived family support (within treatment). Our fifth test will examine if teaching skills to enhance positive family exchanges produces increased family satisfaction (month 4) by increasing positive shared time (within treatment). Finally, we will assess if teaching skills to improve communication increases 4-month family relationship satisfaction by mobilizing more positive partner communications within treatment. No adjustment for inflated Type I error is planned for these six tests.

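### The two primary drinking HLMs leave out the three factors that the urn balances on; prespecifying them is a cheap gain in precision, conditional on the factors being prognostic

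*Combined protocol and SAP*

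**What the plan says.** The Randomization section uses an urn scheme "to balance groups on patient gender, severity of alcohol dependence, and type of CFM (parent versus partner versus other".

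The Aim 2a analysis text says of PDA and PDH: "Two primary alcohol use measures will be considered and aggregated into four monthly values". The random intercept is examined first, followed by conditional models "which will introduce baseline value of the respective drinking measure (PDA or PDH) as a fixed covariate and the random linear time term". Then: "Treatment group will then be entered in level two of the model", with a t-test at .025 per outcome. Cross-level terms are tested "to identify potential time by group interactions in changes in alcohol use". The Statistical power paragraph also names a single covariate, "the baseline dependent measure entered as a fixed covariate". No Aim 2a model lists gender, severity or CFM type.

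The same paragraph explains that "substantial emphasis in this application is placed upon both inferential testing and the estimation and evaluation of effect sizes". It expects 34 B-FIT and 17 TAU patients after 15% attrition.

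The exploratory Aim 2d models enter one moderator at a time with treatment and their product. Continuous moderators are split at the median.

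**The concern.** Balancing allocation on a prognostic factor makes the group difference less variable across possible allocations. A model without that factor leaves its variance in the residual, so the reported standard error does not reflect the precision gained by balancing. In a trial of 51 analysed patients that stresses effect-size estimation, the width of the group interval is a main product, and the design has already done the work needed to narrow it.

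The factors are known before randomisation, so no new data are needed. The choice is protected only if it is made before outcomes are examined by group. The protocol is dated February 2017 and its timeline starts analysis in December 2017.

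**Working it through.** **Inputs from the documents.** Patients: 60 (Participant Enrollment), 40 of them in B-FIT at baseline (Aim 2c), hence 20 in TAU. Attrition 15%. Two-sided alpha .025. Three urn factors, one with three levels.

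**Assumptions not in the documents.** Gender and severity take 1 df each and CFM type 2, so k = 4. R2 is the population share of person-level residual variance that the factors explain after baseline drinking. Urn parameters and factor frequencies are also assumed.

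**The plan's own figures.** 40 x .85 = 34 and 20 x .85 = 17, total 51: reproduced. The stated power of .703 at effect size .20 does not follow from the stated inputs alone. Read as Cohen's d with one value per person, it gives about .06. Read as f with 51 x 4 = 204 uncorrelated values, it gives .705, but then .892 at .25 where the plan has .80. That is a separate matter; nothing below uses .703.

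**Step 1: interval width.** With complete data, the level-two group term behaves like a regression of the person mean on group and baseline, with 51 - 3 = 48 df, or 44 df with the factors. Then

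width ratio (with / without) = sqrt[(1 - R2) x VIF] x t44 / t48,

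where VIF is the variance inflation from residual imbalance. At .025 two-sided, t48 = 2.314 and t44 = 2.321, so (t44/t48)^2 = 1.006.

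**Step 2: VIF and break-even**, R2 = 1 - 1/(VIF x 1.006):

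- Perfect balance: VIF = 1, break-even 0.6%.
- Simulated 2:1 urn of 60 with random loss to 51, several factor mixes: VIF about 1.055 to 1.060, break-even 5.8% to 6.2%.
- Simple randomisation: VIF = 47/43 = 1.093, break-even 9.0%.

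**Step 3: longitudinal check.** A second simulation used four monthly values, random intercept and slope, and 20,000 runs per R2. It computed the group term by the complete-data regression equivalent of the HLM. Against REML fits of 158 data sets (some with convergence warnings), the t statistics correlated .9998.

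| R2 | Step 1 formula, VIF 1.055 | Longitudinal simulation |
|---|---|---|
| 0 | 1.030 | 1.029 |
| .05 | 1.004 | 1.002 |
| .10 | .977 | .974 |
| .20 | .921 | .918 |
| .30 | .862 | .857 |

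Its break-even is 5.4%, hence about 5-6% overall.

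**Step 4: calibration without the factors.** At R2 = .20 the mean model standard error is .300 against a true SD of .291, about 3% too large. Size at nominal .025 is .024, .022, .020 and .016 at R2 of 0, .10, .20 and .30. With the factors it is .023 to .027.

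**Step 5: power, without v with the factors, at assumed d.**

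| d | R2 = 0 | R2 = .10 | R2 = .20 |
|---|---|---|---|
| .25 | .075 v .073 | .075 v .082 | .072 v .090 |
| .5 | .262 v .249 | .262 v .279 | .262 v .317 |
| .8 | .637 v .611 | .640 v .663 | .645 v .716 |

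**Step 6: time-by-group.** At R2 = .20 its standard error is .119 with or without the factors.

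**Minor side point, Aim 2d.** Under linear moderation by a normal variable, a median split keeps 2/pi = .64 of the information. At alpha .05 with 34 v 17, power for the continuous form v the split is .244 v .168 at an assumed slope of .4, and .700 v .474 at .8. A true step at the median reverses this: .478 v .605 at a step of +/-.8.

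**The case against.** The strongest reply is that nothing here is an error. The estimate is unbiased, the test errs on the safe side, and the sign of the benefit depends on an R2 that the documents never give. Severity probably overlaps baseline drinking, which lowers what it can add. At R2 = .10 the half-width moves only from about .69 SD (2.314 x .300) to .68 SD (x .974), and at d = .25 power stays below .10 whichever model is used. All of this stands, and it limits the point to a cheap improvement.

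The simulations also assume normal outcomes, complete months and loss at random. PDA and PDH are bounded, and a three-level CFM factor may leave thin cells among 17 TAU patients. Neither was examined, so the percentages are approximate.

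It can be said that Aim 2d already brings demographic variables and severity into the drinking models. It does so one moderator at a time, with a product term, in exploratory analyses. That does not replace adjustment of the main group comparison.

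The Aim 2a generalized linear models omit the same factors. The calculation here covers only the two primary alcohol measures, and no change to those other models is proposed.

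**Conclusion.** The omission is real and its consequence is modest. If the urn factors are prognostic beyond baseline drinking, the baseline-only models report a group interval somewhat wider than it need be. The gain from adjusting is about 2-3% of interval width at R2 = .10 and 8% at .20; the loss is about 3% at R2 = 0. Break-even is about 5-6% under a plausible urn with 15% loss, and about 0.6-9% across balance assumptions. These figures rest on k = 4 and on R2 as a population share; as an in-sample R2 the variance break-even would be 4/48 = 8.3%.

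A reader might infer more, in three ways that the documents do not support:

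- That leaving out balancing factors biases the comparison or inflates Type I error. It does neither; size falls below nominal.
- That adjusting is sure to raise power. Below the break-even it does not, and no section gives the R2.
- That the two different interviews named for the alcohol use disorder diagnosis show a conflict in the urn's severity variable. No section ties either to the urn, and the unstated severity score is only missing detail.

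The median-split remark is minor: the plan itself calls Aim 2d exploratory and underpowered.

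**What to change.** In both drinking HLMs, prespecify patient gender, CFM type (parent, partner, other) and severity, coded as the urn uses it, as fixed level-two covariates beside baseline PDA or PDH. State the severity coding when doing so. Report the baseline-only model as a sensitivity analysis. Fix this before outcomes are examined by group.

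The cost is SAP wording and up to 4 df. If the factors explain nothing, the group interval is about 3% wider and power falls from .637 to .611 at an assumed d of .8, or from .262 to .249 at .5.

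Optional: in Aim 2d, enter continuous moderators as centred continuous variables with their product with treatment, and keep the median splits for display. This loses power if moderation is a true step at the median.
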